**9.12.2 DEMOGRAPHICS AND BASELINE CHARACTERISTICS ANALYSIS**

Demographics and baseline characteristics will be summarized for each part of the study using appropriate descriptive statistics.

**9.12.3 CONCOMITANT MEDICATIONS/THERAPIES**

Concomitant medications will be summarized for each part of the study. All prior and concomitant medications recorded in the case report form will be coded to all matching Anatomic Therapeutic Classification codes using the most recent version of the WHO Drug Dictionary. Descriptive summaries will be prepared using the coded term. In addition, all concomitant medications recorded in the case report form will be listed.

**9.13 ANALYSES FOR THE OUTCOMES OF THE PART 1 STUDY**

The primary outcome measure of the Part 1 study is Maximum Tolerable Dose (MTD) by maximum percentage of BSA treated, by evaluation of dose-limiting toxicity (DLT) of AMTX-100 CF (1.1% w/w concentration) based on the safety profile.

AEs will be classified by system organ class (SOC) and preferred term (PT) according to the most recent version of MedDRA dictionary. All AEs that met the dose escalation stopping criteria will be summarized using MedDRA SOC & PT and by relationship to the study treatment for the safety population.

[REDACTED]

- [REDACTED]
- [REDACTED]
- [REDACTED]

[REDACTED]

[REDACTED]

[REDACTED]

[REDACTED]

## 9.14 ANALYSES FOR THE OUTCOMES OF THE PART 2 STUDY

### Efficacy Summaries

The efficacy evaluable population will be the primary analysis population for the analysis of the efficacy outcome measures of the Part 2 study. All the primary and secondary outcome measures will be analyzed according to the variable type:

- [REDACTED]

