### 3.3 PHASE II (PART 2) STUDY DESIGN

Phase II (Part 2) of this study is a multi-center, double-blind, randomized, vehicle-controlled study of the safety and efficacy of topically applied AMTX-100 *CF3* in adult patients with Mild to Moderate AD. Sixty (60) subjects will be enrolled in 2 groups of AMTX-100 *CF3* and placebo (vehicle). The subjects will be randomized in a 1:1 ratio, thus thirty (30) subjects will be randomized in each group (Group A: Treatment 1.1% w/w of AMTX-100 *CF3*) and Group B: placebo (vehicle 0% w/w)). Each enrolled subject, after screening and randomization, will receive AMTX-100 *CF3* 1.1% w/w or placebo (vehicle) to be applied twice daily to all treatable AD lesions (excluding the scalp, face, eyes, eyelids, hands, palms, feet, groin, genitals or in the axillae) for 28 consecutive days.

The study groups are as follows:

- **Group A:** AMTX-100 *CF3* dose concentration (1.1% w/w), topically applied twice a day for 28 consecutive days to all treatable AD affected areas
- **Group B:** Placebo (Vehicle) (0% w/w), topically applied twice a day for 28 consecutive days to all treatable AD affected areas

[REDACTED]

[REDACTED]

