## 6 STUDY TREATMENTS

### 6.1 METHOD FOR ASSIGNING ELIGIBLE SUBJECTS TO TREATMENT

In Part 1 of the study, study eligible subjects will be assigned to open-label AMTX-100 CF (in 1.1% concentration), based on a cohort assignment schedule prepared by the contracted CRO. Details of the cohort assignment and assignment of the subject number are provided in [Section 8.11](#) and [Section 4.1.1](#).

Subjects in Part 1 of the study will be assigned sequentially to one of the following treatment groups:

█ [REDACTED]

█ [REDACTED]

█ [REDACTED]

█ [REDACTED]

█ [REDACTED]

After a subject has been determined to be eligible for the treatment in Part 1 of the study, a cohort assignment number will be assigned. Once the cohort assignment number is assigned, it cannot be re-assigned even if the subject is subsequently deemed ineligible or withdraws consent.

[REDACTED]

In Part 2 of the study, study eligible subjects will be randomized based on a randomization schedule prepared by the contracted CRO. Details of the randomization and assignment of the subject number are provided in [Section 8.12](#) and [Section 4.2.1](#).

Subjects will be randomized in a 1:1 ratio to one of the following treatment groups in Part 2 of the study:

- Active Treatment (Group A): AMTX-100 CF3 (1.1% w/w);
- Placebo (Group B): Vehicle ( 0% w/w)

After a subject has been determined to be eligible for the treatment in the study, a randomization number will be assigned. Once the randomization number is assigned, it cannot be re-assigned even if the subject is subsequently deemed ineligible or withdraws consent.

[figure not shown]

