**9.2.2 PHASE II (PART 2) STUDY OUTCOME MEASURES**

**9.2.2.1 Primary Efficacy Outcome Measure:**

- Proportion of responder subjects at Day 28, defined as subjects with both Validated Investigator Global Assessment for Atopic Dermatitis (vIGA-AD™) score of 0 (clear) or 1 (almost clear) (on a 5-point scale) and a reduction of  $\geq 2$  points from baseline

Note: Subjects who receive rescue treatments will be considered non-responders

[REDACTED]

■ [REDACTED]

■ [REDACTED]

■ [REDACTED]

■ [REDACTED]

■ [REDACTED]

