### 9.3 SAMPLE SIZE DETERMINATION AND RATIONALE

**Sample size for Phase I (Part 1):** The sample size of 25 subjects (5 subjects per cohort) for Phase I of this study is selected on the basis of clinical judgment and not based on statistical power calculation. The number of subjects is deemed adequate to provide clinically meaningful descriptive results consistent with study objectives.

**Sample size for Phase II (Part 2):** The sample size of 60 subjects for Phase II of this study is selected on the basis of clinical judgment and not based on statistical power calculation. The number of subjects is deemed adequate to provide clinically meaningful results consistent with study objectives.

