## 9.8 ANALYSIS POPULATIONS

The details of the analysis populations to be used for the study are described in the below sections.

[REDACTED]

[REDACTED]

[REDACTED]

[REDACTED]

[REDACTED]

[REDACTED]

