### 9.11 TYPE I ERROR RATE ADJUSTMENT

This is an early phase study and there is no need for adjustment of Type I error rate.

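### Part 2 efficacy is analysed primarily in the efficacy evaluable population; unless that set holds every randomised subject, exclusions after randomisation may bias the comparison

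*Protocol*

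**What the plan says.** Protocol section 9.14 (Efficacy Summaries) names the primary population for Part 2: "The efficacy evaluable population will be the primary analysis population for the analysis of the efficacy outcome measures of the Part 2 study". The definitions belong in section 9.8, which opens with "The details of the analysis populations to be used for the study are described in the below sections"; everything after that sentence is blacked out in the public copy. The list of tests in 9.14 and most of 9.12 are blacked out too. The supplied SAP covers Part 1 only, so it defines no Part 2 population.

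Other readable text that bears on the point:

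- **Design (3.3):** "The subjects will be randomized in a 1:1 ratio, thus thirty (30) subjects will be randomized in each group".
- **Primary endpoint (9.2.2.1):** "Proportion of responder subjects at Day 28", where response is a vIGA-AD score of 0 or 1 with a fall of at least 2 points from baseline. A note adds: "Subjects who receive rescue treatments will be considered non-responders".
- **Missing data (9.9):** nothing is imputed, and summaries use observed data only.
- **Blinding (9.5):** subjects, investigators and the sponsor and CRO staff managing the study are blinded in Part 2.
- **Withdrawal (5.2):** listed reasons include adverse events, the subject's own choice, and excessive deviations as judged by the investigator or sponsor.

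**The concern.** Randomisation makes the two arms comparable only if the subjects analysed are the subjects randomised. An evaluability rule that acts after randomisation can take out subjects for reasons that differ between an active cream and its vehicle and that also relate to outcome, such as local reactions, poor adherence or lack of benefit. The remaining subjects are then no longer a randomised comparison, and the response rates can differ without any drug effect, or a real effect can be masked.

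This is related to, but not the same as, a missing Day 28 score. An evaluability rule can drop subjects who do have a score. Conversely, the observed-data rule in 9.9 drops subjects with no score even when the population is all randomised subjects. Dealing with one leaves the other open.

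With 30 subjects per arm, the handling of a few subjects can decide how the result reads.

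**Working it through.** **The plan's own figure.** Part 2 has 60 subjects at 1:1, and 60/2 = 30 per arm, which agrees with 3.3. The 60 was "selected on the basis of clinical judgment and not based on statistical power calculation", so there is no power, response rate or dropout figure to reproduce. Nothing in the documents is contradicted arithmetically.

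**Inputs.** From the documents: 30 per arm and a binary responder endpoint at Day 28. Assumed, because the readable text gives none: response rates, exclusion shares and a two-sided 0.05 level. On alpha, section 9.11 says only "This is an early phase study and there is no need for adjustment of Type I error rate".

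**Step 1: expected bias when there is no true effect.** Let p be the true response rate in both arms and d the share of an arm's non-responders excluded. The observed rate is

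p / [p + (1 − p)(1 − d)].

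With d = 30% in active and 10% in vehicle:

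| True rate p | Active | Vehicle | Spurious difference |
|---|---|---|---|
| 10% | 0.10/0.73 = 13.7% | 0.10/0.91 = 11.0% | +2.7 points |
| 20% | 0.20/0.76 = 26.3% | 0.20/0.92 = 21.7% | +4.6 points |
| 30% | 0.30/0.79 = 38.0% | 0.30/0.93 = 32.3% | +5.7 points |

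At p = 20% there are 24 expected non-responders per arm, so these shares mean about 7 exclusions in active (24 × 0.3 = 7.2) and 2 in vehicle (24 × 0.1 = 2.4). In whole subjects: 6/30 in each arm, with 6 active and 1 vehicle non-responders excluded, becomes 6/24 = 25.0% v 6/29 = 20.7%, or +4.3 points. Swapping the exclusion shares between arms reverses the sign. Equal shares give no bias in this no-effect case.

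**Step 2: effect on a test.** Take 30 per arm, the same true rate in both arms, a share q of active non-responders excluded and none in vehicle. Exact type I error of the pooled two-proportion z test:

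| True rate | q = 0 | q = 10% | q = 20% | q = 30% |
|---|---|---|---|---|
| 10% | 5.4% | 5.0% | 5.8% | 7.3% |
| 20% | 4.9% | 5.5% | 6.6% | 8.9% |
| 30% | 4.9% | 5.6% | 7.0% | 9.7% |

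At a true rate of 20%, false positives favouring active rise from 2.5% (q = 0) to 8.2% (q = 30%).

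**Step 3: illustrative tables.** Excluded subjects are counted as non-responders in the all-randomised rows.

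| Analysis | Result | Difference | Pooled z | Fisher |
|---|---|---|---|---|
| All randomised | 10/30 v 4/30 | 20.0 points | p = 0.067 | p = 0.125 |
| 5 active non-responders dropped | 10/25 v 4/30 | 26.7 points | p = 0.024 | p = 0.032 |
| All randomised | 12/30 v 4/30 | 26.7 points | p = 0.020 | p = 0.039 |
| 6 vehicle non-responders dropped | 12/30 v 4/24 | 23.3 points | p = 0.062 | p = 0.078 |

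Losing five or six non-responders from one arm can move a result across 0.05 in either direction.

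**Step 4: loss unrelated to arm or outcome.** This mainly costs power. At assumed rates of 10% v 40%, power is 78% with 30 per arm, 73% with 27 and 68% with 24.

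**The case against.** The strongest reply is that the definition is blacked out, and a blacked-out definition is not a fault of the plan. The evaluable set could be close to all randomised subjects (for example, everyone treated with a post-baseline assessment) or close to a per-protocol set. The contents page shows blacked-out entries under 9.8, while the readable text names only a safety and an efficacy evaluable population, so an all-randomised set may be defined there. All of this stands.

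A reader might infer that the plan does exclude randomised subjects and has no all-randomised analysis. The documents do not support that. The Protocol's abbreviation list has Per Protocol but no intent-to-treat term, which is weak evidence when the definitions are hidden. Nor does section 6.1 establish exclusion. Its sentence "Once the randomization number is assigned, it cannot be re-assigned even if the subject is subsequently deemed ineligible or withdraws consent" concerns re-use of randomisation numbers, and the same rule is given for the open-label Part 1 cohort numbers. It shows that ineligibility or withdrawal after randomisation is foreseen, not that such subjects leave the analysis.

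There are real safeguards. Blinding limits exclusions driven by knowledge of treatment, although reactions or lack of benefit caused by treatment can still differ between arms. The rescue rule captures many treatment failures as non-response, but it can act only on subjects who remain in the analysed set.

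The assumed bias is also modest against sampling error. The standard error of the difference at 30 per arm is √(2 × 0.2 × 0.8/30) = 10.3 points at 20% response and √(2 × 0.3 × 0.7/30) = 11.8 points at 30%, so 4.6 and 5.7 points are each just under half of one standard error. That is fair. But more subjects would reduce sampling error and would not reduce this bias. That the study is early phase with no power calculation lowers the stakes; it gives no reason to prefer the evaluable set.

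**Conclusion.** The point holds conditionally. What is certain is that the readable plan makes an efficacy evaluable set primary for the only randomised comparison and does not say that this set is all randomised subjects. What cannot be determined is whether anyone is excluded, by what rule, and whether an all-randomised analysis sits alongside.

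If there are exclusions and they differ by arm, the expected bias with no true effect is about 3 to 6 points for true rates of 10% to 30% with 30% v 10% of non-responders excluded (4.6 points at 20%). With 30% excluded from the active arm only, type I error rises from about 5% to 7–10%. The response rates, exclusion shares and 0.05 level are all assumptions, so these figures illustrate sensitivity and do not predict this trial's result. The change is worth making because it is cheap and removes a doubt that blinding and the rescue rule only reduce.

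**What to change.** State in section 9.14 and in the Part 2 SAP that all randomised subjects, analysed in the arm to which they were randomised, are the primary population for the Part 2 efficacy outcomes, and that the efficacy evaluable population is supportive.

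For the primary responder endpoint, add that a subject without a Day 28 vIGA-AD score counts as a non-responder, and make section 9.9 consistent with this. Renaming the population alone would not be enough, since 9.9 would still remove these subjects. The rule follows the same logic as the existing treatment of rescue.

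If the blacked-out definition already equals all randomised subjects, only the Day 28 rule is needed, and the set is better called by that name.

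The cost is a few sentences, one extra table and possibly slightly lower response rates. The sample size need not be revisited, because it rests on no power calculation. Counting missing scores as non-response is itself an assumption and can shift the difference if missingness is unequal between arms, so the number missing should be reported by arm.

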### Safety Summaries

Similar to the Part 1 of the study, AEs will be coded using MedDRA. Treatment Emergent AE's (TEAE) are defined as events with an onset on or after the first randomized treatment. TEAEs will be summarized by treatment groups, system organ class, and preferred term. The following TEAE summaries will be provided:

- [REDACTED]
- [REDACTED]
- [REDACTED]
- [REDACTED]

## 10 ADVERSE EVENTS (DEFINITIONS AND REPORTING)

The Investigator is responsible for the detection and documentation of events meeting the criteria and definition of an AE or SAE, as provided in this protocol. During the study when there is a safety evaluation, the Investigator or site staff will be responsible for detecting, documenting, and reporting AEs and SAEs as detailed in this section of the protocol.

### 10.1 ADVERSE EVENTS

An adverse event (AE) is defined as any unfavorable or unintended sign, symptom, or disease that occurs or is reported by the subject to have occurred, or a worsening of a pre-existing condition. An AE may or may not be related to the study treatment.

AEs will be elicited through direct questioning and subject reports. Any abnormalities in visit evaluations, physical examination findings or laboratory results that the Investigator believes are clinically significant to the research subject and that occurred after initiation of the first study treatment will be reported as AEs. Abnormal findings that are NOT clinically significant should not be recorded as an AE.

#### 10.1.1 REPORTING OF ADVERSE EVENTS

Report initiation for all AEs and SAEs will begin at the time of the first study treatment administration and continue up until the final study visit. All events will be followed to resolution or until they are considered as non-clinically significant event.

All AEs must be recorded in the subject's medical records and on the CRF. AEs will be reported using customary medical terminology along with the following information: the onset and end dates, whether the event is considered to be an SAE (see [Section 10.2](#)), the impact the event had on study treatment (see [Section 10.1.2](#)), the CTCAE grade (intensity) of the event (see [Section 10.1.3](#)), the causality of the event (see [Section 10.1.4](#)), whether treatment was given as a result of the event (see [Section 10.1.5](#)), and the outcome of the event (see [Section 10.1.6](#)).

#### 10.1.2 IMPACT ON STUDY TREATMENT

The impact the event had on the study treatment will be assessed as either: none, study treatment interrupted, study treatment discontinued, or not applicable. The "not applicable" assessment will be used only when the subject is no longer in the treatment phase of the protocol, or if the outcome of the event was "death".

#### 10.1.3 SEVERITY (INTENSITY) ASSESSMENT

The guidelines outlined in CTCAE v5.0 will be used for assessing the severity or intensity of the event. The general guidelines for assessing the AE grade appear below. Full guidelines may be obtained at <http://evs.nci.nih.gov/ftp1/CTCAE>.

**Table 10-1: CTCAE v5.0 General Guidelines**

Grade	Description
Grade 1	Mild; asymptomatic or mild symptoms; clinical or diagnostic observations only; intervention not indicated.
Grade 2	Moderate; minimal, local, or noninvasive intervention indicated; limiting age-appropriate instrumental activities of daily living (ADL)*.
Grade 3	Severe or medically significant but not immediately life-threatening; hospitalization or prolongation of hospitalization indicated; disabling; limiting self care ADL†.
Grade 4	Life-threatening consequences; urgent intervention indicated.
Grade 5	Death related to AE.

\*Instrumental ADL refer to preparing meals, shopping for groceries or clothes, using the telephone, managing money, etc.

†Self care ADL refer to bathing, dressing and undressing, feeding self, using the toilet, taking medications, and not bedridden.

-Common Terminology Criteria for Adverse Events (CTCAE), v5.0: November 27, 2017

#### 10.1.4 CAUSALITY ASSESSMENT

Adverse events will be assigned a relationship (causality) to the study treatment. The Principal Investigator must review each AE and make the determination of relationship of the event to the study treatment. Relationship of AEs to study treatment will be classified as follows:

- 1. Definitely related:** This category applies to those AEs that the Investigator feels are incontrovertibly related to the study treatment. An AE may be assigned an attribution of definitely related if or when it meets all of the following criteria: (1) it follows a reasonable temporal sequence from administration of the study treatment; (2) it could not be reasonably explained by the known characteristics of the subject's clinical state, environmental or toxic factors, or other modes of therapy administered to the subject; (3) Disappears or is decreased upon discontinuation of the study treatment; (4) it follows a known response pattern to treatment with the study treatment.
- 2. Probably related:** This category applies to those AEs which, after careful medical consideration at the time they are evaluated, are felt with a high degree of certainty to be related to the study treatment. An AE may be considered probable if or when (must have three): (1) it follows a reasonable temporal sequence from administration of the study treatment. (2) It could not readily have been produced by subject's clinical state, environmental or toxic factors, or other therapies administered to the subject. (3) Disappears or is decreased upon discontinuation of the study treatment. (4) It follows a known response pattern to treatment with the study treatment.
- 3. Possibly related:** This category applies to those AEs which, after careful medical consideration at the time they are evaluated, are judged unlikely but cannot be ruled out with certainty to the study treatment. An AE may be considered possible if or when (must have two): (1) it follows a reasonable temporal sequence from administration of the study treatment. (2) It could not readily have been produced by subject's clinical state, environmental or toxic factors, or other therapies administered to the subject. (3) Disappears or is decreased upon discontinuation of the study treatment. (4) It follows a known response pattern to treatment with the study treatment.

4. **Unlikely related:** In general this category can be considered applicable to those AEs which, after careful medical consideration at the time they are evaluated, are judged likely to be unrelated to the study treatment. An AE may be considered unlikely if or when (must have two): (1) it does not follow a reasonable temporal sequence from administration of the study treatment. (2) It could not readily have been produced by subject's clinical state, environmental or toxic factors, or other therapies administered to the subject. (3) Disappears or is decreased upon discontinuation of the study treatment. (4) It does not follow a known response pattern to treatment with the study treatment.
5. **Unrelated:** This category applies to those AEs which, after careful consideration at the time they are evaluated, are clearly and incontrovertibly due to extraneous causes (disease, environment, etc.) and determined with certainty to have no relationship to the study treatment.

[figure not shown]

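### The adverse event categories 'Possibly related' and 'Unlikely related' overlap in both lead-in and criteria, so the boundary between them is left to the investigator's habit

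*Protocol*

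**What the plan says.** Protocol section 10.1.4 has the Principal Investigator place every adverse event in one of five categories. Each category has a lead-in sentence describing the judgement. The first four also have a list of four criteria.

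- **Item 2, Probably related.** "An AE may be considered probable if or when (must have three"; the four criteria are plausible timing, no ready alternative cause, improvement on stopping, and a known response pattern.
- **Item 3, Possibly related.** The lead-in covers events that "are judged unlikely but cannot be ruled out with certainty to the study treatment". The criteria are the same four, with a lower count: "An AE may be considered possible if or when (must have two): (1) it follows a reasonable temporal sequence from administration of the study treatment", and so on.
- **Item 4, Unlikely related.** The lead-in covers events that "are judged likely to be unrelated to the study treatment". The criteria begin "An AE may be considered unlikely if or when (must have two): (1) it does not follow a reasonable temporal sequence". Criterion (4) is likewise reversed. Criteria (2) and (3) are not: they read "It could not readily have been produced by subject's clinical state, environmental or toxic factors, or other therapies administered to the subject" and "Disappears or is decreased upon discontinuation of the study treatment", as in items 2 and 3.
- **Item 5, Unrelated.** This is the only category that requires certainty that there is no relationship.

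In section 9.13, the Part 1 events that met the dose escalation stopping criteria "will be summarized using MedDRA SOC & PT and by relationship to the study treatment".

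**The concern.** A graded causality scale works only if adjacent categories describe different judgements. Here an investigator who thinks a link to the cream improbable, but cannot exclude it, fits the lead-ins of both item 3 and item 4. One who thinks a link reasonably possible finds the category name but no lead-in that says so: the descriptions pass from strong confidence in a relationship (item 2) directly to an improbable one (item 3).

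At stake is the consistency of the relationship coding across investigators and sites. Section 9.13 tabulates by that coding the events that matter most in Part 1, those that met the escalation stopping criteria.

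**Working it through.** The plan gives no figure on this point, so the check compares the lead-ins and then counts where the criteria overlap.

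**Lead-ins.** Judging a relation unlikely (item 3) and judging an event likely to be unrelated (item 4) express the same opinion. Item 3 adds that the relation cannot be excluded with certainty. That does not separate it from item 4, because only item 5 claims certainty; anything short of item 5 is also not excluded with certainty.

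**Criteria.** Let T, A, D and K each be 1 if the attribute is present and 0 if not: plausible timing (T), no ready alternative cause (A), improvement on stopping (D), known response pattern (K). There are 2 × 2 × 2 × 2 = 16 patterns.

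- Item 3 score: s = T + A + D + K.
- Item 4 score as written: u = (1 − T) + A + D + (1 − K).
- Item 4 score with criteria (2) and (3) reversed: u′ = 4 − s.

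Reading the requirement of two as at least two:

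| | Meets item 3 | Meets item 4 | Meets both |
|---|---|---|---|
| Item 4 as written | 11 | 11 | 8 |
| Item 4 criteria (2) and (3) reversed | 11 | 11 | 6 |

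The 11 for item 3 is 6 patterns with two attributes, 4 with three and 1 with four. The 8 that meet both as written are:

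- two attributes (5 patterns): TA, TD, AD, AK, DK, with u = 2, 2, 4, 2, 2;
- three attributes (2 patterns): TAD and ADK, with u = 3 and 3;
- all four attributes (1 pattern): u = 0 + 1 + 1 + 0 = 2.

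The last three patterns also meet the count for Probably related, and the pattern with all four attributes matches the four criteria of Definitely related. In the other direction, two patterns (timing only, known response pattern only) have s = 1 and u = 1 and so meet the criteria of neither Unlikely related nor any related category.

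With criteria (2) and (3) reversed, item 4 is met when 4 − s ≥ 2, that is s ≤ 2. Both items are then met exactly when s = 2, which gives 6 patterns. The overlap with Probably and Definitely related disappears, and so do the two unplaced patterns.

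Reading the requirement as exactly two gives 4 patterns meeting both as written, and 6 with the reversal.

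Correcting item 4's criteria alone therefore leaves every two-attribute event eligible for both categories, with only the lead-ins to decide, and those say the same thing. Correcting the item 3 lead-in alone leaves the 8 of 16 criteria overlap untouched.

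**The case against.** **The criteria are permissive.** They say when an event *may* be placed in a category. An investigator can see plausible timing and improvement on stopping, still think a link improbable, and not exclude it. This stands: item 3's lead-in is in tension with its criteria but does not contradict them.

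**The name and the falling count of criteria (four, three, two) show what item 3 is for.** They do show the intention. They do not rescue the boundary, because item 4 also asks for two criteria and its lead-in repeats item 3's judgement.

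**A reader might infer that the related/unrelated split of adverse events is undetermined, or that the Part 1 dose conclusion is affected.** The documents do not support either. No two-way split is visible; taking Possibly/Unlikely as that cut is an outside convention. The lists of event summaries and the DLT definition are redacted, so a grouping rule may exist and causality may or may not enter the DLT definition. For the same reason the plan cannot be faulted for not saying which categories count as related.

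**A reader might also put a size on this from one reclassified subject:** 1/5 = 20 percentage points in a Part 1 cohort, or 1/30 = 3.3 points in a Part 2 arm. Those figures follow from the group sizes whatever the cause of reclassification, and nothing says how often it would occur.

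**The use is descriptive.** The Part 1 SAP plans no hypothesis test (section 5) and no inferential safety statistics (section 8.2). Part 2 investigators are blinded (protocol section 9.5), so inconsistent coding should not systematically favour an arm. This limits the consequence to noise in a descriptive table.

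**Conclusion.** The point holds for the boundary between Possibly and Unlikely related. Both lead-ins are fully visible, so redaction does not explain the overlap. The item 3 lead-in is one cause; item 4's unreversed criteria and the shared two-of-four threshold are the others.

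The size is the overlap in the rule: 8 of 16 patterns as written and 6 of 16 after reversing item 4's criteria (2) and (3), on the at-least-two reading (4 and 6 on the exactly-two reading). These counts treat each pattern as one case. They are not event frequencies, since real events will not be spread evenly over the patterns.

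The consequence that can be shown is that the summary by relationship in section 9.13, read as using the five categories of 10.1.4, depends on investigator habit at this boundary.

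**What to change.** Make three changes together in section 10.1.4:

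1. Reword the item 3 lead-in to say that a causal relation is reasonably possible but not established with the confidence that item 2 asks for. Do not require that another cause be plausible: that would conflict with item 3's own criterion (2), which counts the absence of a ready alternative cause in favour of the category.
2. Reverse criteria (2) and (3) of item 4, so that all four of its criteria point away from the study treatment.
3. State that when an event meets the criteria of both items, the judgement in the lead-in decides.

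The cost is a few sentences in 10.1.4 and the matching CRF completion guide, plus a check that events already classified under the present text remain comparable with those classified afterwards. Sample size and data collection do not change.
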